Furthermore, a review by Nitsche et al. (2008) presented the behavioral, cognitive and side effects of tDCS in over 90 studies that had been conducted between 1998-2008. In summary, these reports have indicated that tDCS is a noninvasive procedure with strong promise for improving learning and memory across a wide population. The majority of tDCS studies that were reviewed reported no side effects. Approximately one third of these studies reported mild itching or tingling under the electrodes as the most severe and common side effect. Of more than 90 studies, less than 10 of these papers indicated that subjects experienced headache, and in most cases only one participant reported headache in those studies.

In our collaborator [name] laboratory, using Protocol #468198-3, a tDCS experiment was completed in 21 individuals. No adverse events have occurred during this experiment. Sensations reported across subjects included an itching or tingling sensation at the electrode location, a prickling sensation that felt like small needles, or mild heat sensations at the electrode site. In all of these cases, the reported pain level on a scale from 1 (no pain) to 10 (extreme pain) never exceeded a value of 6. The median self reported pain value was a 2. At the end of the procedure, self-report measures showed no adverse effects on mood at the end of the procedure compared with the reported measures before the session.

Since the Nitsche review in 2008, the field of tDCS has quickly expanded, and to date a PubMed search of "transcranial direct current stimulation" results in 2705 published articles. In these studies there have been almost no reported seizures, loss of consciousness or persistent neurologic signs or symptoms. Therefore, the evidence to date suggests that the main risk associated with tDCS is a mild burning/tingling sensation. After approximately 10 years of experience and hundreds of publications with the technique, there have only very rarely been reports of serious adverse effects in subjects who have participated, including those studies involving multiple sessions (a rare case report was recently published by Ekici (2015) that described a seizure in a boy diagnosed with spastic tetraparesis induced after 3 consecutive days of direct stimulation to the motor cortex). The likelihood of inducing seizures is low due to the fact that tDCS current strengths are almost always administered at least an order of magnitude lower than that required to induce epileptiform activity, even during gamma oscillations (Bikson et al., 2016; Bikson et al., 2004). For example, our colleagues, [name] and [name] at the University of Pennsylvania, reported that 10 sessions of tDCS (with 2 weeks of 5 sessions over consecutive days) did not result in any serious adverse effects, and the repeated exposure to stimulation did not

PROTOCOL TITLE: The Effects of Transcranial Direct Current Stimulation on the Neuronal Mechanisms of Cognitive Control in Schizophrenia

result in an increased incidence of adverse effects when compared to shorter-term studies (Richmond et al., 2013).

Given that itching, tingling, and burning tend to be the most likely adverse effects associated with noninvasive stimulation studies, protocols have been outlined to help minimize the risk of skin damage or burning. In a paper by Loo et al. (2011) they outlined a protocol to address the potential risk of skin burns during tDCS experiments. They suggested that skin burns are attributed to drying out of electrodes and/or uneven skin abrasion. In order to prevent skin burns they suggested incorporating a few simple steps, including screening subjects for any skin conditions, inspecting skin at stimulation site for cuts, rash, etc. prior to placing electrodes, cleaning but not abrading skin prior to electrode placement, disinfecting electrodes, dampening sponges with saline when using single-use sponge electrodes (and monitoring them so that they do not dry out), periodically questioning subjects about sensations at the electrode site, stopping stimulation or adjusting electrodes if the subject reports discomfort, and inspecting skin for redness or damage following stimulation. In order to minimize skin burning in our experiments, we have incorporated these steps into our protocol (see 11. Procedures). Loo et al. (2011) reported that, by following these procedures, they were able to conduct over 2000 experiments without the incidence of any skin burns. This is the most extensive report on 2 mA stimulation. In addition, they reported that skin burns are usually preceded by pain. By asking the subjects to report any instance of pain, as well as periodic sensation questionnaires, the occurrence of skin burns can be minimized.

Noninvasive stimulation techniques such as tDCS have also been used safely to study cognitive function in several patient populations, including Parkinson's Disease (Boggio et al., 2006), stroke (Jo et al., 2009), Alzheimer's Disease (Boggio et al., 2009), and schizophrenia (reviewed by Kekic et al., 2016). Most relevant to this protocol, Brunelin et al. (2012) conducted a pilot study to explore the safety and efficacy in refractory schizophrenia. In this experiment patients received 2 mA of current for 20 minutes twice a day with a 3-hour interval, across 5 consecutive days. Patients improved on measures of symptoms, particularly in auditory hallucinations. No adverse events occurred. Patients only described a transient mild tingling or a slight itching sensation associated with the onset of stimulation. Additionally, the tolerability of tDCS in childhood-onset schizophrenia has been assessed (Mattai et al., 2011). In this study, patients received 2 mA or sham stimulation in 20-minute sessions, across 10 sessions (over 2 weeks). tDCS was well tolerated in all subjects, and no serious adverse events were reported. Again, the most common effect reported was tingling and itching, and a few reports of mild fatigue.

The great majority of tDCS studies in schizophrenia have targeted the DLPFC. Most studies have observed reduced positive and/or negative symptoms, with no studies reporting severe adverse events (reviewed by Kekic et al., 2016). These studies involve a range of patients, including patients with childhood-onset schizophrenia, catatonic schizophrenia, and treatment-resistant schizophrenia. There have been no reports of serious adverse effects, and no reports of seizures in any of these patient studies.

PROTOCOL TITLE: The Effects of Transcranial Direct Current Stimulation on the Neuronal Mechanisms of Cognitive Control in Schizophrenia

Finally, the risk of excitotoxic damage is not applicable to tDCS. Stimulation levels of 1 or 2 mA do not directly induce firing in cells that are not spontaneously active. Instead, it has been shown in animals that tDCS increases spontaneous neuronal firing rates only to a moderate degree and did not reach the threshold for excitotoxicity (Bindman et al., 1964). At 1 or 2 mA, it has been shown that tDCS does not increase levels of serum neurone-specific enolase (Nitsche et al., 2003; Nitsche and Paulus, 2001) a sensitive marker of neuronal damage (Steinhoff et al., 1999). In rats, only at doses 100 times higher than those used in humans was neural pathology evident. Whereas 800 mA is used in humans for electroconvulsive shock therapy (ECT), which is intended to induce seizures, we only intend to use a maximum of 2 mA. Therefore, it is highly unlikely that this dose will produce seizures in a non-epileptic population. Furthermore, we would like to re-emphasize that non-invasive stimulation techniques such as tDCS and tACS are not at all similar to ECT, and therefore, the risks are quite different. In addition, tDCS is also quite different from, and considered less invasive than, other stimulation techniques such as transcranial magnetic stimulation (TMS). The risks associated with tDCS and tACS have been shown to be minimal.

Some additional potential risks have been identified, and although these events rarely (if ever) occur, every precaution will be made to prevent these risks. These risks include tissue damage, changes in mood, and electrical shock.

Plan For Minimizing Risk To Subjects :

Normal patient handling procedures are followed to eliminate risks. The subjects will be able to communicate with the investigators at all times. The subject's emotional state and mood will be assessed before and after stimulation; and physical sensation will also be monitored with a questionnaire administered before, during, and after the stimulation procedure (see above for details). The subject can ask to stop the experiment at any time for any reason. Likewise, the experimenter may stop the experiment at any time if the subject reports experiencing any pain or discomfort. When stopping the stimulation, the current will be gradually ramped down using the safe stop mode in order to avoid any unpleasantness or painfulness associated with abruptly aborting stimulation. It is also important to note that individuals may respond differently across tDCS conditions. Therefore, we will monitor all participants closely even when they have completed previous visits with no adverse effects. In the unlikely event that a subject experiences serious side effects or injury due to the experiment, the experimenter will call 911, and these details will be immediately communicated to the IRB. We have identified the following potential risks associated with tDCS and address them in turn:

I. Skin Damage or Irritation: Nitsche et al. (2003) suggest that there may be a slight risk of skin damage or irritation resulting from tDCS stimulation. With the exception of Iyer et al. (2005) who reported transient redness at the stimulating electrode site in two men who had recently shaved their heads, we have encountered no reports of skin damage or irritation in any of the tDCS literature. The possibility of skin damage resulting from electrode heat has also been tested using stimulation parameters comparable to those outlined in this protocol. None of these results have indicated skin damage due to electrode heat. Furthermore, we will be using saline-soaked electrodes, or we will use electrode paste, for our study, which minimizes the possibility of chemical reactions at the electrode-skin

PROTOCOL TITLE: The Effects of Transcranial Direct Current Stimulation on the Neuronal Mechanisms of Cognitive Control in Schizophrenia

interface and resultant skin damage. The scalps of each subject will be visually inspected immediately before stimulation. Any identified irritation or evidence of recent shaving of the head will postpone or terminate that subject's participation in the study. Subjects will also be asked to remove any jewelry that may come into contact with the electrodes. Subjects will be encouraged at the beginning of the tDCS procedure to report any pain or discomfort that they may encounter throughout the procedure. Any such reports, or evidence of redness or irritation of the scalp, will result in the immediate termination of stimulation. Additionally, subjects will be screened for latex allergies to prevent allergic reactions to the electrodes. If allergic reactions are noted at any time, stimulation will be ceased, and electrodes will be removed. Overall, these methods for prevention of skin damage follow the suggestions of Loo et al. (2011, see above).

To avoid burning the patient, there is a recommended limit of 0.1 mA/cm^2 for DC current applications (per the device manual). For example, using electrodes with a surface area of 35 cm^2 with a current of 1 mA applies a current density of 0.02857 mA/cm^2 . It is possible that subjects may experience pain at lower levels of current, and therefore, we will closely monitor subjects' responses on the questionnaires. To avoid permanent injury of tissue, current density should not be higher than 25 mA/cm^2 at any given electrode site. This limit is far above the limit for thermal effects of the current density. Note that the maximum current in this protocol is 2 mA , and the surface area of the Starstim PISTIM electrodes is 3.14 cm^2 . Other Starstim stimulating electrode options include the SPONSTIM electrodes in either 8 cm^2 or 25 cm^2 . Thus, the maximal current density used in this protocol will range from $0.080 - 0.64 \text{ mA/cm}^2$. Therefore, the maximum current density will always be set below the recommended limit to avoid any skin burning or damage.

II. Tissue Damage and Discomfort : To minimize any possible tissue damage we have subjects fill out a tDCS sensation questionnaire form throughout the tDCS procedure. This questionnaire allows us to monitor what the subjects are physically feeling at the electrode sites. This will be given at the following time points: 1 minute after start of tDCS, 5 minutes after start of tDCS, and 20 minutes after tDCS. If at any time the subject reports a sensation level of 7 on a 10-point scale, we immediately discontinue the experiment. We will also administer a subjective mood questionnaire before and following experimentation. Any significant changes in answers provided following the experiment will result in further assessment every 15 minutes until subjects return to near baseline state. (also see above "Skin damage or irritation" for further details).

III. Pain: At very strong, focal current density can result in pain. We will be using large electrodes and passing weak electrical current. As previously stated, with protocols similar to ours, most subjects report only mild, transient tingling at the stimulation site. Any subject report of pain resulting from tDCS will result in immediate termination of stimulation.

IV. Alterations in Mood or Affect: There is evidence that tDCS can result in changes in mood and concentration. While no studies have reported negative affect resulting from DC stimulation, several studies have reported improved mood after tDCS. It should be noted that, in these studies, stimulation was applied for significantly longer durations. Studies designed to investigate the safety aspects of non-invasive brain stimulation have reported no significant changes in mood as

PROTOCOL TITLE: The Effects of Transcranial Direct Current Stimulation on the Neuronal Mechanisms of Cognitive Control in Schizophrenia

measured with the VAMS (Visual Analog Mood Scales) and no significant changes in measures of fatigue when comparing stimulation to sham. Therefore, we do not anticipate any changes in mood or affect resulting from our study. To further ensure that subjects are not experiencing alterations in mood or mental state that could potentially debilitate them, we will administer a subjective mood questionnaire before and following experimentation. Any significant changes in answers provided following the experiment will result in further assessment every 15 minutes until subjects return to near baseline state.

V. Electrical Shock: As with any contact between persons and electrical apparatuses, there is a slight possibility of electrical shock. To our knowledge, no studies have reported any incidents of significant electrical shock resulting from DC stimulation, and we do not anticipate this event occurring in our experiment. To help ensure the prevention of electrical shock, we will avoid conducting experiments near potential liquid spills. Further, we will ensure that subjects are not in contact with any potential conductors other than those specified in the experimental design. This measure greatly reduces the likelihood that electrical shock will result from short-circuiting or inadequate insulation. In the very unlikely event that the subject experiences a shocking sensation, the current will be first be ramped down, turned off, and then the electrodes will be removed.

There is the possibility of an electrostatic discharge by touching the patient (for example the patient's head) or the DC-STIMULATOR PLUS. Having an electrostatic discharge while electrodes are attached to a subject may cause a discharge current to flow through the electrodes leading to a shock sensation similar to that experienced in everyday life. Such currents are not dangerous but they are unpleasant. As such, we will avoid touching the patient during stimulation.

The output circuit of the constant current source of the DC-STIMULATOR PLUS is equipped with an electrical fuse that limits the current to 5 mA. Therefore, in any faulty condition and during normal operation, current will be ramped down and then turned off.

There is a potential of a strong stimulus to be delivered if the electrodes are disconnected while current is flowing. Therefore, electrodes will not be disconnected while current is flowing. Instead, current will be ramped down until it is off completely before electrodes will be removed.

VI. Avoiding Electrode Placements Outside the Head: For safety reasons, we will never use bipolar stimulation on any other part of the body apart from the head. Although not reported in any tDCS studies, it is plausible that bipolar stimulation setups could potentially harm the heart if electrodes are set up in a manner that would pass current across the heart. Similarly, we will avoid electrode setups that could lead to the stimulation of the brain stem and cerebellum (vagus nerve). Care will always be taken during electrode placement to ensure that areas outside the head are not stimulated.

VII. Contraindications for Subjects with Electrical Support Systems: Stimulation from tDCS may interfere with pacemakers or implanted brain stimulators. Accordingly, subjects will be carefully screened for pacemakers or

PROTOCOL TITLE: The Effects of Transcranial Direct Current Stimulation on the Neuronal Mechanisms of Cognitive Control in Schizophrenia

brain stimulators prior to the initiation of the study. Subjects with pacemakers or brain stimulators will not be allowed to participate.

VIII. Availability of PIs: With the above safeguards in place, the tDCS stimulation procedures described above are expected to be safe and well-tolerated. As an added precaution, the PI ([name].) will be available on call during each session to answer any questions for research staff. A licensed physician, [name] will review the case details of any adverse event and determine whether any modifications to the protocol are needed in order to further minimize risks. If he deems it necessary, he will have the authority to stop a tDCS research session or to halt further tDCS studies.

In the unlikely event that a subject experiences serious side effects or injury due to the experiment, these details will be immediately communicated to the IRB. These subjects will also be provided with the necessary medical care. Our personnel will call 911 upon a medical emergency, such as a seizure, while ensuring that the subject does not cause further harm to him or herself.

Specifically, we will report serious adverse events as well as other unanticipated problems to the IRB within five days of becoming aware of such an event, provided that the event or problem occurred at UC Davis, suggests that the research places subjects or others at a greater risk of harm than was previously known or recognized, was unanticipated, and was related or possibly related to the research. In the report, we will either justify why no changes to the protocol or consent form are needed or attach proposed modifications to the report. Responses to all requests from the IRB for further information will be made within 10 working days of receipt of the request.

IX. Seizure: Although risk of seizure is very low, steps will be taken to minimize this risk. Any subjects with a history of epilepsy or seizures will be excluded. Furthermore, any subjects who are currently (less than 1 month prior to enrollment) taking the antipsychotic clozapine will be excluded as this antipsychotic associated with the greatest risk for seizures (Devinsky et al., 1991)

13) Potential Benefits to Subjects

Subjects may receive some benefit from participation. Previous studies indicate that tDCS may produce transient improvements in cognitive performance. For instance, reports have demonstrated improvements in working memory performance in healthy adults (Fregni et al., 2005; Keeser et al., 2011) as well as patients with schizophrenia (Hoy et al., 2014). Improved social cognition after tDCS stimulation of the DLPFC has been observed in schizophrenia as well (Rassovsky et al., 2015).

14) Sharing of Results with Subjects

N/A

15) Provisions to Protect the Privacy Interests of Subjects

The data and/or specimens will be labeled with a code that the research team can link to personal identifying information when acquired. The code sheet will be secured and kept separate from the dataset. All data will be stored on password-

PROTOCOL TITLE: The Effects of Transcranial Direct Current Stimulation on the Neuronal Mechanisms of Cognitive Control in Schizophrenia

protected computers and/or networks. Information regarding personal information will only be requested from the subject by the recruiter and experimenter. No personal identifiers will be attached to data. During the experiment, the experimenter will thoroughly explain all procedures to ensure that the subjects feel at ease with the procedures.

16) Economic Burden to Subjects

N/A

17) Drugs or Devices

This study uses the Starstim device. Although not approved by the FDA, this device is specifically designed for non-invasive stimulation and EEG research, and is widely used across academic institutions worldwide. This device has demonstrated safety, and is also CE-Certified with approval in Europe. This device does not involve greater than minimal risk. A brochure for this product has been attached. The device will be stored in a locked laboratory that is supervised by investigators on the protocol during working hours. All authorized investigators will be trained on the procedures outlined in this protocol for the proper use of this device on subjects.

In addition to the manuals, brochures and other info re: this device are attached to this submission.

I confirm that all investigational devices will be labeled in accordance with FDA regulations and stored and dispensed in such a manner that they will be used only on subjects and be used only by authorized investigators.

18) [ClinicalTrials.gov](#) Registration

FDAAA 801 establishes penalties for Responsible Parties who fail to comply with [ClinicalTrials.gov](#) registration or results submission requirements. Penalties include civil monetary penalties and, for federally funded studies, the withholding of grant funds.

Section 1: NIH Funded Studies

If yes to BOTH, the study must be registered on [Clinicaltrials.gov](#).

Yes	
	This study is funded by the NIH . (If this study is not funded by NIH, go to Section 2.)
	One or more human subjects will be prospectively assigned to one or more interventions (which may include placebo or other control) to evaluate the effects of those interventions on health-related biomedical or behavioral outcomes.

Section 2: Studies subject to FDA jurisdiction

If yes to ANY the study must be registered on [Clinicaltrials.gov](#).

Ye s	
---------	--

PROTOCOL TITLE: The Effects of Transcranial Direct Current Stimulation on the Neuronal Mechanisms of Cognitive Control in Schizophrenia

	This is a prospective clinical study of health outcomes in human subjects that compares an intervention with an FDA-regulated device against a control. This is not a small clinical trial to determine the feasibility of a device, or a clinical trial to test prototype devices where the primary outcome measure relates to feasibility and not to health outcomes.
	This is a pediatric postmarket surveillance of a device as required under section 522 of the Federal Food, Drug, and Cosmetic Act.
	This is a controlled clinical investigation, other than a phase I clinical investigation, of a drug subject to section 505 of the Federal Food, Drug, and Cosmetic Act or to section 351 of the Public Health Service Act.

To view a flowchart describing applicable clinical trials subject to FDA jurisdiction click [here](#).

Section 3: Publishing the results

If yes to BOTH the study must be registered on Clinicaltrials.gov.

Yes	
	This study prospectively assigns people or a group of people to an intervention, with or without concurrent comparison or control groups, to study the cause-and-effect relationship between a health-related intervention and a health outcome.
	The PI has access to and control over all the data from the clinical trial and has the right to publish the results of the trial and plans to publish the results in a journal that follows the ICMJE recommendations .

This requirement includes studies of behavioral interventions.

Section 4: Registration on Clinicaltrials.gov is not required

Yes	
	I have read sections 1-3 above and registration on clinicaltrials.gov is not required for this research.

19) References

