“Stimulation Only” or “Stimulation and EEG” electrodes may be used (see electrode chart above). Note, for ease of these experiments, the “Stimulation Only” electrodes will be used in most cases. For these electrodes, sponge electrodes will be moistened (with saline), prior to placement on the subject’s scalp. Alternatively, “Stimulation and EEG” electrodes (PISTIM) will be applied using conductive electrode gel. See chart above for electrode sizes and specification. Up to 8 electrodes may be used at any given time (in addition to external/reference electrodes. See above). Only scalp electrode sites designated on the Starstim cap will be used. The cap only uses standard electrode sites from the 10-20 system.

tDCS stimulation (~25 minutes). During this phase, participants will first receive a few minutes of training on the DPX task and complete a brief practice session. Subjects will also be familiarized with the working memory task (see below). After practice, stimulation (or sham stimulation) will begin.

Following the practice session, subjects will undergo sham with task, DLPFC with task, sham without task, DLPFC without task, or SMC active stimulation. The order of the conditions will be fully counterbalanced across subjects. This experiment involves five tDCS visits, and may include tDCS at any of the designated scalp electrode sites in the Starstim cap. Each stimulation visit will be separated by at least 24-48 hours.

Subjects will receive up to 20 minutes of tDCS stimulation or sham, in addition to a few seconds of ramp up and ramp down time at the beginning and end of each session, using the Starstim device. All subjects will receive up to 2.0 mA for the first 30-60 s of stimulation. Current strength will be ramped down, and then reduced to 0.0-0.1 mA in subjects receiving sham stimulation for the remainder of the session. The active stimulation subjects will continue to receive up to 2.0 mA stimulation. Many participants can feel the onset of the stimulation (which leads to a brief tingling or itching sensation), but people cannot generally feel the continued stimulation beyond one minute. By beginning both the active and sham stimulation conditions with a period of stimulation, we can ensure that participants will not

PROTOCOL TITLE: The Effects of Transcranial Direct Current Stimulation on the Neuronal Mechanisms of Cognitive Control in Schizophrenia

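### The protocol promises current density below its 0.1 mA/cm² burn limit, yet its own stated maximum runs from 0.080 to 0.64 mA/cm²

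*Protocol*

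**What the plan says.** Everything needed stands in one paragraph of section 12, part I:

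- The burn limit: "To avoid burning the patient, there is a recommended limit of 0.1 mA/cm^2 for DC current applications (per the device manual").
- A second, much higher limit for a different harm: "To avoid permanent injury of tissue, current density should not be higher than 25 mA/cm^2 at any given electrode site". The protocol adds that this one lies well beyond the level at which heating matters.
- The maximum current is 2 mA.
- The electrodes: "the surface area of the Starstim PISTIM electrodes is 3.14 cm^2", and "Other Starstim stimulating electrode options include the SPONSTIM electrodes in either 8 cm^2 or 25 cm^2".
- The result: "the maximal current density used in this protocol will range from" 0.080 to 0.64 mA/cm².
- The conclusion: "Therefore, the maximum current density will always be set below the recommended limit to avoid any skin burning or damage".

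Section 7 permits up to 2 mA, both in the table of stimulation parameters and in the description of the stimulation session. Neither place ties the current to the electrode type or says whether 2 mA is the total or the current per electrode. On the number of electrodes, section 7 says "Up to 8 electrodes may be used at any given time". For each stimulating electrode, the electrode chart in section 7 refers the user to a current safety chart, which is not reproduced.

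**The concern.** The upper end of the stated density range is above the limit that the conclusion says is never reached. The paragraph is the protocol's only quantitative assurance against skin burns. Read literally, it tells staff that any listed electrode at up to 2 mA is under the burn limit.

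Other parts of the protocol lean on that assurance. Section 7 lets current, duration and sites be changed during the study, on the footing that safety and tolerability will not be affected. Section 10 treats safety monitoring as not applicable because risk is minimal. Section 17 has investigators trained on the procedures in this document. Someone relying on section 12 could run 2 mA through a single PISTIM electrode and believe it compliant.

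**Working it through.** **Inputs**, all from section 12, part I: burn limit 0.1 mA/cm²; maximum current 2 mA; electrode areas 25, 8 and 3.14 cm². The maximum of 8 electrodes comes from section 7. (The stimulation table there also shows a figure of 39, but its columns are broken in the text available, so 8 is used.)

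**Formula.** Density = current / electrode area. The protocol's own example, 1 mA over 35 cm², gives 1/35 = 0.02857 mA/cm², so the formula is the one it uses.

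**Reproducing the stated range.** With the full 2 mA through one electrode, 2/25 = 0.080 and 2/3.14 = 0.637. These are the two ends of the protocol's range, so its range assumes a single electrode carrying the whole current.

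**Comparison with the limit, one electrode:**

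| Electrode | Density at 2 mA | Ratio to 0.1 | Density at 1 mA | Ratio to 0.1 | Largest current at 0.1 mA/cm² |
|---|---|---|---|---|---|
| 25 cm² | 2/25 = 0.080 | 0.8 | 1/25 = 0.040 | 0.4 | 2.5 mA, so the 2 mA maximum governs |
| 8 cm² | 2/8 = 0.25 | 2.5 | 1/8 = 0.125 | 1.25 | 0.8 mA |
| 3.14 cm² | 2/3.14 = 0.637 | 6.4 | 1/3.14 = 0.318 | 3.2 | 0.314 mA |

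The 1 mA columns are for illustration. Section 2 gives 1 to 2 mA as typical of tDCS, but the procedures set only a ceiling.

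**Which limit is meant?** Only 0.1 is called a recommended limit and only 0.1 is tied to burning. The conclusion repeats both ideas. The 25 mA/cm² figure concerns permanent tissue injury, and the protocol itself places it far beyond thermal effects, so it cannot serve as the burn limit.

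**Can splitting the current rescue the claim?** Assume 2 mA is a total, is shared evenly, and returns through the same number and type of electrodes:

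- 8 cm² sponges: 2/0.8 = 2.5, so 3 per polarity. Density is 2/3/8 = 0.083. That is 6 in all, within 8.
- PISTIM only: 2/0.314 = 6.4, so 7 per polarity. Density is 2/7/3.14 = 0.091. That is 14 in all, above 8. Four per polarity carry at most 4 × 0.314 = 1.26 mA; at 1 mA they run at 1/4/3.14 = 0.080.
- Mixed: seven PISTIM at 0.091 with one 25 cm² return at 0.080 makes 8 and carries 2 mA, if mixing is allowed. The protocol does not say.

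If 2 mA is per electrode, splitting changes nothing and 0.25 and 0.64 stand.

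**Margin to the tissue-injury limit.** 25/0.637 = 39, 25/0.25 = 100, 25/0.080 = 312. All three electrodes are far below it.

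**The case against.** The best counter-argument is that the quoted limit, not the dose, may be the mistake. Part V of section 12 (Electrical Shock) describes the safeguards of a DC-STIMULATOR PLUS, whereas sections 7 and 17 say the study uses Starstim. The worked example uses a 35 cm² electrode, which is not among the listed stimulating electrodes. This suggests, without proving it, that the 0.1 figure was carried over from another device's manual. If so, leading with 2.5 and 6.4 times the limit overstates the practical problem. That possibility stands, and it is why confirming the limit comes first in the fix. It does not make the paragraph consistent.

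Second, the protocol does tie current to electrode type by reference, through the safety chart. The chart may hold the small electrodes to lower currents. That reduces practical risk, but it would make the 0.64 figure wrong and would not reconcile it with the conclusion.

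Third, other safeguards exist. Stimulation stops at a sensation rating of 7 and on pain, and for skin signs the text is firm: "Any such reports, or evidence of redness or irritation of the scalp, will result in the immediate termination of stimulation". Burning is also listed among the risks. These are real mitigation, but they act after symptoms or signs appear, while a density cap acts before.

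Finally, section 7 says stimulation-only electrodes will be used in most cases. Both sponges are described that way, so the usual choice may be the compliant 25 cm² sponge. Nothing says which sponge is usual.

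**Conclusion.** The contradiction is certain: the limit, the range and the conclusion cannot all be true. On the protocol's own basis of 2 mA through one electrode, two of the three listed electrodes exceed the stated burn limit, by factors of 2.5 and 6.4, and both still exceed it at 1 mA.

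Confidence is high for the contradiction, not for a change of dose. Over-exposure of any participant is not shown: 2 mA is a ceiling, the chart is unseen, and splitting may apply if 2 mA is a total. No endpoint or analysis is touched. The correction is still necessary, because this is a false numerical assurance on participant safety that staff could act on.

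**What to change.** 1. Confirm in the Starstim documentation which density limit applies, and cite the source.
2. State whether the 2 mA maximum is the total current or the current per electrode.
3. If 0.1 mA/cm² applies, add a rule to the stimulation-parameter table in section 7: the current through each electrode, return electrodes included, must not exceed 0.1 mA/cm² times its area. That means up to the 2 mA protocol maximum for 25 cm², 0.8 mA for 8 cm² and about 0.31 mA for 3.14 cm². Total current may be split across electrodes.
4. If another limit applies, replace the 0.1 figure with it.
5. In either case, revise section 12 so that the limit, the 0.080 to 0.64 range and the concluding sentence agree. While doing so, align the description of the electrodes as large (part III, Pain) with the electrodes used, since section 7 describes the PISTIM by its small area.

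**Cost.** A text amendment, with no added participants or visits and no electrode excluded. If 0.1 applies, small electrodes used singly are limited to 0.8 or about 0.31 mA. Running them at 1 to 2 mA needs split current and more electrodes, and PISTIM alone cannot reach 2 mA with 8 electrodes. Splitting also gives up some of the focal stimulation for which the PISTIM is offered. If the Starstim limit is 0.64 mA/cm² or higher, only the quoted limit and the wording change.
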